8.3.2. Study Outcomes

AESIs, as listed below and in line with the definitions and code lists that for most of the AESIs have been created for the ACCESS project (<https://zenodo.org/communities/vac4eu/>), will be identified, with a date of diagnosis, using predefined validated algorithms (where available), based on diagnosis codes (with procedure and/or pharmacy dispensing codes and/or limited to specific medical care settings if applicable to the outcome). Only codes tagged as “narrow” (i.e., specific) will be used. Whenever no “narrow” codes are available in any applicable coding system, “possible” codes will be used instead to identify the corresponding AESI. It is possible that some AESIs will not have “narrow” codes in some coding systems. Therefore, some AESIs may not be assessable in all data sources. The impact of different provenance of data (hospital, general practitioner's diagnoses) and algorithms on the outcome frequency will be assessed and described in the feasibility assessment.

For the first feasibility assessment, the following rare and prioritised AESIs will be studied. The list includes encephalitis, including acute disseminated myelitis (ADEM) and meningoencephalitis; Guillain-Barré syndrome; transverse myelitis; multiple sclerosis, including optic neuritis; immune thrombocytopenia; anaphylaxis; cardiac inflammatory disorders, including myocarditis and pericarditis; stress cardiomyopathy; coronary artery disease, including acute myocardial infarction; deep vein thrombosis; pulmonary embolism; disseminated intravascular coagulation; non-haemorrhagic stroke; haemorrhagic stroke; thrombocytopenia and acute hepatic failure. As per EMA PRAC request, exacerbation of asthma will also be included in the feasibility assessment. For subsequent feasibility and final report, all AESIs will be analysed.

8.3.3. Evaluation of Safety Outcomes

The sponsor has created a list of AESIs based on current knowledge of the Ad26.COV2.S vaccine. [Table 1](#) lists and explains the AESIs to be ascertained in the study with specific risk windows. Background incidence rates for most of the data sources and AESIs are available on the VAC4EU dashboard <https://vac4eu.org/covid-19-tool/>. Definitions and codes are available on Zenodo (<https://zenodo.org/communities/vac4eu/>).

Table 1: AESI-Specific Risk Windows and Washout Periods for Patient Inclusion in the Study

Body System	AESI	Disease-specific washout period before the index date	Disease-specific risk window following the index date
Nervous and central nervous system	Encephalitis, including ADEM and meningoencephalitis	365 days	1-42 days
	Guillain-Barré Syndrome	365 days	1-42 days
	Transverse myelitis	365 days	1-42 days
	Bell's palsy	365 days	1-42 days
	Multiple sclerosis, including optic neuritis	365 days	1-365 days
	Sensorineural Hearing loss	365 days	1-60 days
	Generalised convulsion	365 days (w/o epilepsy) 90 days (w/o non-epileptic seizures)	1-14 days
Immune system	Autoimmune thyroiditis	365 days	1-365 days
	Immune thrombocytopenia	365 days	1-42 days
	Type 1 diabetes mellitus	Any time prior*	1-365 days
	Acute aseptic arthritis	365 days	1-365 days
	Anaphylaxis	90 days	0-2 days
Cardiac system	Cardiac inflammatory disorders, including myocarditis and pericarditis	365 days	1-28 days
	Microangiopathy	365 days	1-28 days
	Heart failure	365 days	1-28 days
	Stress cardiomyopathy	365 days	1-28 days
	Coronary artery disease, including acute myocardial infarction	365 days	1-28 days
	Arrhythmia	365 days	1-14 days
Blood and lymphatic system disorders	Deep vein thrombosis	365 days	1-28 days
	Pulmonary embolism	365 days	1-28 days
	Disseminated intravascular coagulation	365 days	1-28 days
	Non-haemorrhagic stroke	365 days	1-28 days
	Haemorrhagic Stroke	365 days	1-28 days
	thrombocytopenia	365 days	1-28 days
	peripheral thrombosis	365 days	1-28 days
	Sinus thrombosis	365 days	1-28 days
	Thrombotic Thrombocytopenia syndrome	365 days	1-28 days
	Composite: venous thrombosis	365 days	1-28 days
	Composite: arterial thrombosis	365 days	1-28 days
Composite: strokes	365 days	1-28 days	
Renal system	Acute kidney failure	365 days	1-14 days
Hepatic system	Acute hepatic failure	365 days	1-14 days
Respiratory system	Exacerbation of asthma	365 days	1-14 days

Abbreviations: ADEM = Acute disseminated encephalomyelitis, AESI = adverse event of special interest, All non-acute events are considered to have a washout period of 365 days. * For diabetes mellitus which is a chronic condition we will use any time prior for washout.

Exacerbation of asthma ascertainment will require the definition of an asthma cohort and identifying exacerbations of asthma within that cohort.

The asthma cohort will be defined by having:

- a code for asthma and;
- at least 2 prescriptions for an inhaled corticosteroid within 5 years before the index date.

Among this asthma cohort, an exacerbation of asthma was defined by having:

- At least 1 prescription of a systemic glucocorticosteroid during the defined risk window or;

- At least 1 hospitalisation for asthma during the defined risk window.

The date of this event will be the date of the first prescription of a systemic glucocorticosteroid or the admission date for hospitalisation for asthma, whichever comes first.

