 - Individuals who have a prior history of thrombotic events and/or thrombocytopenia,
 - Prior COVID-19 infection,
 - Individuals with a prior history (ever) of the specific event more than a year before start of follow-up.

These results will be compared to COVID-19 vaccine unexposed individuals and, to individuals exposed to other types of COVID-19 vaccines (mRNA or adenovirus-based platforms) or compared to a control window within the same individual.

Endpoints

Feasibility Assessment

The endpoints for the feasibility assessment, including a monitoring phase, are:

- Quality assessment of data that has been extracted from the source data banks (completeness, logic and benchmarking between data sources and against external data)
- The number of doses and uptake of different COVID-19 vaccines by calendar time
- The demographic and morbidity characteristics of individuals receiving the different COVID-19 vaccines
- Algorithms for AESI identification (including exacerbation of asthma)
- Incident rates and cumulative incidence (risk) of the selected AESIs and corresponding 95% confidence intervals (CIs), without prespecified risk windows
- Risk factors for AESI.

Safety Evaluation Study

The primary endpoints for the safety evaluation study are to estimate the risk of the selected AESIs listed below among individuals vaccinated with the Ad26.COV2.S vaccine and in corresponding unexposed individuals and individuals exposed to other types of COVID-19 vaccines (split between mRNA platform-based vaccines and adenovirus-based platforms), or during a control window within the same individual.

The contractual agreements with data partners will stipulate the ability to allow newly identified AESIs to be incorporated into the study objectives, and the current protocol that will be used for governance approvals will state that additional AESI may be added. Each data access provider is responsible to inform the appropriate ethics boards of these amendments.

Acute events (events expected to be recorded within 60 days of vaccination).

- The incidence of anaphylaxis within 0-2 days.

- The incidence of generalized convulsion, arrhythmia, acute kidney failure and acute hepatic failure within 1-14 days.
- The incidence of the following events within 1-28 days

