 - thrombotic events (microangiopathy including capillary leak syndrome), disseminated intravascular coagulation, deep vein thrombosis, pulmonary embolism, cerebral vein thrombosis, peripheral thrombosis, thrombosis with thrombocytopenia and ischemic strokes, acute coronary syndrome (acute myocardial infarction, unstable angina, and new onset angina),
 - bleeding events including haemorrhagic stroke (no subarachnoid),
 - composite endpoint: Venous thrombosis (including pulmonary embolism and deep vein thrombosis)
 - composite endpoint: Arterial thrombosis (including acute coronary syndrome and ischemic stroke),
 - composite endpoint: stroke (including haemorrhagic and non-hemorrhagic stroke)
 - heart failure, and stress cardiomyopathy.
- The incidence of immune/inflammatory events: encephalitis (including acute demyelinating encephalomyelopathy and meningoencephalitis), Guillain-Barré Syndrome, Bell's palsy, immune thrombocytopenia, thrombocytopenia, transverse myelitis and cardiac inflammatory disorders (including myocarditis and pericarditis) within 1-42 days.
- The incidence of sensorineural hearing loss within 1-60 days.
- The incidence of asthma exacerbation within 1-14 days.

Non-acute events (events expected to be recorded >60 days after vaccination)

- The incidence of new-onset autoimmune thyroiditis, multiple sclerosis, acute aseptic arthritis, and type 1 diabetes mellitus within 1-365 days.

Newly identified AESI may be incorporated into the list of AESI to be investigated by the current study if a safety signal occurs.

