will be the day the first dose of the corresponding COVID-19 vaccination was received. This date in the unexposed group will be a day when an individual did not receive a COVID-19 vaccine dose and randomly chosen by calendar matching to the start date of the corresponding Ad26.COV2.S exposed individual (i.e., a random day during the same week that the matching individual in the exposed cohort receives the Ad26.COV2.S vaccine).

Individuals in the Ad26.COV2.S exposed cohort will be individually matched to one individual in the concurrent unexposed cohort and to one individual in each active comparator cohorts on key clinical variables (exact age, sex, previous COVID-19 infection and presence of one or more risk factors for severe COVID-19 [e.g., cancer, sickle cell disease, obesity, chronic kidney disease, chronic respiratory disease, human immunodeficiency virus infection], and month of vaccination (using calliper if needed)) at the index date.

[figure not shown]
Three sets of matched cohorts of individuals who meet all inclusion and exclusion criteria will be considered as follows:

- Recipients of a first Ad26.COV2.S dose matched to recipients of the first dose of a viral vector COVID-19 vaccine (AstraZeneca vaccine)
- Recipients of a first Ad26.COV2.S dose matched to recipients of the first dose of an mRNA COVID-19 vaccine (Pfizer-BioNTech or Moderna)
- Recipients of a first Ad26.COV2.S dose matched to unvaccinated individuals at the index date (individuals in this cohort may later become eligible to enter the exposed cohorts if vaccinated with a COVID-19 vaccine).

For the matched exposed cohorts, the index date (time zero) will be the date of the corresponding COVID-19 vaccine. For the unvaccinated individuals, the index date will be assigned as the index date of the matched exposed individual (see [Figure 2](#)). Additional details regarding matching will be included in the SAP.

Follow-up for unexposed persons is censored when the individual receives a COVID-19 vaccine. In a sensitivity analysis, vaccination with other non-COVID-19 vaccines will also be an exclusion and censoring event.

Figure 2: Schematic Overview of the Cohort Study Design

AESI = adverse event of special interest; COVID-19 = coronavirus disease 2019; FU = follow-up; SARS-CoV-2 = severe acute respiratory syndrome coronavirus-2.

Note: In the figure 1 year enrolment refers to the inclusion criterion to have at least 12 months of data available before the index date.

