8.2.3. Study Duration and Follow-Up

Feasibility Assessment

For the feasibility assessment, the study period will start on the date when each participating country begins with the Ad26.COV2.S vaccine or the latest date when the individual is registered in the data source (plus 365 days) or born and will end a maximum of 12 months thereafter. Individuals will be followed until the earliest of the following dates: death, end of data availability, individual exit from the data source, or the completion of the period.

Safety Evaluation Study

- For the SCRI design, the study period will start at the date of the start of the pre-vaccination control window (Table 1). Follow-up ends at the earliest of the following: death, end of data availability, individual withdrawal of the study, end of the post-vaccination risk or control window, or receipt of another COVID-19 vaccine. In a sensitivity analysis, follow-up will be censored upon receipt of other vaccines (non-COVID-19 vaccine). We will also compare the Ad26.COV2.S vaccine with active comparators with 1) only 1-dose strategy and 2) a 2-dose strategy. Figure 1 shows the different periods considered for the SCRI design.
- For the cohort design, the study period will start at the date when each participating country will begin with the Ad26.COV2.S vaccine and will end at the end of data availability at each data source. For the cohort design, the follow-up will start at the beginning of the vaccination risk window, as detailed in Table 1 and ends at the occurrence of each AESI, death, end of data availability, individual exits the database, after one year of follow-up, receipt of a

COVID-19 vaccine (unexposed cohort only), receipt of a different COVID-19 vaccine from the one granting access to the study (exposed cohorts only). For the vaccine-exposed comparator groups, a second dose of the same corresponding vaccine will be allowed (more details will be provided in the SAP). In a sensitivity analysis, follow-up in the cohort study will be censored upon receipt of other vaccines (non-COVID-19 vaccine). Another sensitivity analysis will also compare the Ad26.COV2.S with active comparators with (1) a 1-dose strategy and (2) a 2-dose strategy. For the subgroup analysis of subjects without COVID-19 at the start of risk window, patients will be censored if they develop COVID-19 during follow-up.

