8.2.5. Exclusion Criteria

For the feasibility assessment, there will be no exclusion criteria.

Individuals will be excluded from the safety evaluation study if:

- They have been vaccinated with any other COVID-19 vaccines before starting each risk window.

- Record of the specific AESI during the specific corresponding washout periods for the SCRI and cohort analyses. Individuals with such acute diagnoses before the AESI-specific washout periods will not be excluded. For clarification, when one AESI will be investigated, any history or prevalence of other AESIs will not be excluded. [Table 1](#) shows the specific washout periods for each AESI.

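### For AESIs whose risk window starts on day 1, the vaccination day is in neither the washout nor the risk window, so a case first recorded that day stays eligible and can be counted from a later record

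*Protocol*

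**What the plan says.** - **Index date.** In the vaccinated cohorts it "will be the day the first dose of the corresponding COVID-19 vaccination was received" (Protocol, cohort design, section 8.1.2.2). Figure 1 likewise labels the index date as time 0 for the SCRI.
- **Washout.** The Table 1 column is headed "Disease-specific washout period before the index date". Most entries are 365 days; anaphylaxis has 90 days, and type 1 diabetes has any time prior.
- **Risk window.** The next column is headed "Disease-specific risk window following the index date". Every entry starts on day 1 apart from anaphylaxis. Section 7 shows the same contrast: "The incidence of sensorineural hearing loss within 1-60 days" against "The incidence of anaphylaxis within 0-2 days".
- **Exclusion.** The only exclusion based on AESI history is "Record of the specific AESI during the specific corresponding washout periods for the SCRI and cohort analyses" (section 8.2.5).
- **Start of counting.** In the cohort, "the follow-up will start at the beginning of the vaccination risk window, as detailed in Table 1" (section 8.2.3), and section 8.1.2.2 defines the start of follow-up as the time from which outcomes are counted.
- **Repeat records.** Section 8.1.2.1 accepts that one episode may be captured twice through re-admission, but discusses only a risk-window event reappearing in the control window.
- **Left open.** Section 8.3.3.1 defers to the SAP whether an event is dated by diagnosis or first retrievable symptom, and makes case validation optional.

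**The concern.** A washout is there so that an event counted after vaccination is a new one. If it stops at day -1 and counting starts at day 1, a diagnosis entered on day 0 does neither job: it does not remove the person and it is not counted. The person starts day 1 as if event-free. Section 8.3.2 draws outcomes from both hospital and GP diagnoses, so one episode may leave several dated records, and the next one can look like an incident case shortly after vaccination.

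In the SCRI such carry-over records would fall mostly in the nearer risk window rather than in the later post-vaccination control window, which pushes the ratio up. In the cohort they would add prevalent cases to whichever arm has more day-0 recording. For a safety study the stake is a modest false excess for some AESIs, chiefly those with 14-day windows: convulsion, arrhythmia, acute kidney failure, acute hepatic failure and asthma exacerbation.

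**Working it through.** **Step 1. Where day 0 falls.** With the washout before the index date, its last day is -1.

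| AESI (Table 1) | Washout | Risk window | Day 0 in washout? | Day 0 in risk window? |
|---|---|---|---|---|
| Acute kidney failure | 365 days | 1-14 | no | no |
| Deep vein thrombosis | 365 days | 1-28 | no | no |
| Guillain-Barré syndrome | 365 days | 1-42 | no | no |
| Sensorineural hearing loss | 365 days | 1-60 | no | no |
| Multiple sclerosis | 365 days | 1-365 | no | no |
| Anaphylaxis | 90 days | 0-2 | no | yes |

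**Step 2. Do other stated rules cover it?** The SCRI separates control and risk windows by a buffer. In the main analysis the control window comes after the risk window, so that buffer also lies after the risk window and does not reach day 0. The protocol states no exclusion for a day-0 record and no first-record rule that spans day 0.

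**Step 3. Size in the SCRI.** The protocol gives no figure for this, so the inputs are assumptions:
- the true ratio is 1, with ordinary daily rate r;
- day-0 recording is k times r;
- a share q of day-0 cases is recorded again in the risk window and none in the control window;
- both windows last L days.

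The risk window then holds Lr + qkr records and the control window Lr, so the expected ratio is 1 + qk/L.

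| L (days) | k=1, q=0.25 | k=1, q=1 | k=3, q=1 | k=5, q=1 |
|---|---|---|---|---|
| 14 | 1.018 | 1.071 | 1.214 | 1.357 |
| 28 | 1.009 | 1.036 | 1.107 | 1.179 |
| 42 | 1.006 | 1.024 | 1.071 | 1.119 |
| 60 | 1.004 | 1.017 | 1.050 | 1.083 |
| 365 | 1.001 | 1.003 | 1.008 | 1.014 |

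If k is below 1, for instance 0.5 with q=1, the 14-day figure falls to 1 + 0.5/14 = 1.036.

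**Step 4. Direction in the cohort.** The gap applies to both arms. Taking q=1 in each, with k1 in the Ad26.COV2.S arm and k0 in the comparator, the ratio is (L + k1)/(L + k0).
- Equal recording (k1 = k0): the ratio is 1, with no bias.
- k1=3, k0=1: 17/15 = 1.13 for 14 days and 368/366 = 1.005 for 365 days.
- k1=0.5, k0=1: 14.5/15 = 0.97 for 14 days, that is, below 1.

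**Step 5. After the change.** If a day-0 record excludes the person, no day is uncovered and the term qk/L becomes 0. Anaphylaxis needs no change.

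**The case against.** **That carry-over records will be counted.** A reader might infer that the next record is always taken as a new event. The protocol does not say so. Event dating is left to the SAP, and dating by onset or first record would place a day-0 case on day 0 and keep it out. Section 8.3.3 already dates an asthma hospitalisation by admission. This stands: the defensible statement is that such a record can be counted. It does not remove the point, because the eligibility and exclusion rules are fixed in this protocol and leave the person in.

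**That the intent is already clear.** The washout is defined as serving to identify incident cases, and the prior-history subgroup is described as more than a year before follow-up starts, which hints at a look-back ending at day 1. For the SCRI, the abstract starts follow-up at the pre-vaccination control window, so a day-0 record is at least observed. None of this is an exclusion rule, and Table 1 says otherwise. Figures 1 and 2 are not available here, so how they draw day 0 could not be checked.

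**That a marked upward bias is shown.** A reader might also infer that vaccination-day contact makes k well above 1. No figure supports that. The amendment log mentions a healthy vaccinee effect, and section 8.3.1 notes that in the Netherlands several vaccines were given outside traditional care settings, so k could be below 1. The formula also leaves out the opposite bias described in section 8.1.2.1, repeats of risk-window cases in the control window. Both objections stand.

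**That the active-comparator results are affected in the same way.** Those arms also have a vaccination day as index date, so the gap is shared and should largely cancel.

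**That an exclusion anchored at vaccination harms the SCRI.** A 365-day exclusion ending at the index date would remove cases in the pre-vaccination control window. That is true, but Table 1 and section 8.2.5 already have this problem as written; the remedy has to be worded so as not to repeat it.

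**Conclusion.** The gap is real and follows directly from Table 1 and section 8.2.5: for every AESI except anaphylaxis, a person first recorded on day 0 is neither excluded nor counted that day, and a later record of the same episode can be taken as incident.

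The consequence is probably small. With a true ratio of 1, k=1 and every case re-recorded in the risk window, the SCRI ratio is inflated by at most about 1.07, 1.04 and 1.02 for 14-, 28- and 42-day windows. For the 365-day non-acute events, where the cohort is the primary design, the effect is negligible. It grows only if records cluster on day 0, and shrinks if k is below 1, if few cases are re-coded, or if the SAP's dating rule catches them. In the cohort it matters mainly against the unexposed group, with a direction that depends on differential day-0 recording. Starting the risk window on day 1 is not itself the fault; the fault is that the washout stops short of day 0. This is a worthwhile tidy-up rather than a threat to the study's conclusions.

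**What to change.** 1. In Table 1 and section 8.2.5, state that for AESIs with a day-1 start, a record of that AESI on the index date also excludes the person from that AESI's analysis, in all cohort arms and in the SCRI.
2. In the SCRI with a pre-vaccination control window, add this as a stand-alone day-0 exclusion. Keep the AESI washout before the start of the control window, as the abstract's SCRI follow-up text has it, so that control-window cases are not removed.
3. Report day-0 counts by AESI and vaccine descriptively, so that same-day events remain visible.

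Cost: a sentence in each of two places, one clarification for the pre-vaccination SCRI, and one descriptive table. The downside is that a few true same-day onsets that would have been re-coded later leave the ratio. Little is lost, because day-0 records themselves are not counted under the present rules.
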